### **8.4. Packaging and Labeling**

The label(s) for IP will include sponsor name, address and telephone number, the protocol number, IP name, dosage form and strength (where applicable), amount of IP per container, lot number, expiry date (where applicable), medication identification/kit number, dosing instructions, storage conditions, and required caution statements and/or regulatory statements, as applicable. Additional information may be included on the label as applicable per local regulations.

### **8.5. Investigational Product Accountability and Disposal**

Celgene (or designee) will review with the investigator and relevant site personnel the process for Investigational Product return, disposal, and/or destruction including responsibilities for the site vs. Celgene (or designee).

The sponsor (or its designee) will deliver IP with the “Investigational Product Delivery Form” to the IP storage manager at the study site at the start of the study and thereafter as necessary. The IP storage manager will confirm the amount of IP received and submit the “Investigational Product Receipt Form” to the sponsor.

At the end of the study and when needed, the IP storage manager will return all of the unused IP, partially used IP, and empty bottles with the “Investigational Product Return Form” to the sponsor. The sponsor (or designee) will deliver the “Investigational Product Collection Form” to the IP storage manager. If any IP is missing or damaged, the sponsor should be notified immediately. The IP storage manager will document this in the “Investigational Product Return Form,” and the investigator will record this information in the source documents.

## **8.6. Investigational Product Compliance**

The IP storage manager will manage the IPs following the instructions in the “Operating Procedure for Handling and Management of IPs” provided by the sponsor.

The IP storage manager will record receipt of IP from the sponsor, stock of IP at the study site, usage of IP by each subject, and return of unused drug to the sponsor or the disposition of IP. These records include the date, IP names/codes, quantity, lot numbers, and the subject number. The IP storage manager will also record whether the subject received IP at the dose specified in the protocol and whether IP supplied by the sponsor was appropriately managed and stored. Following completion of the study, the IP storage manager will sign and date these records verifying their accuracy. The IP storage manager will retain the original records, and copies of the records are to be submitted to the sponsor.

The investigator is responsible for accounting for all IPs that are issued to and returned by the subject during the course of the study. The investigators will instruct the subjects to manage IP by themselves, and return all unused drugs, if any due to missed doses or other reasons, including empty bottles to the study site.

## 9. CONCOMITANT MEDICATIONS AND PROCEDURES

### 9.1. Permitted Concomitant Medications and Procedures

In general, the use of any concomitant medication/therapies deemed necessary for the care of the subject is permitted.

Prophylactic antiemetics will be withheld until the subject has experienced  $\geq$  Grade 1 nausea or vomiting. The subject may then receive prophylactic antiemetics at the discretion of the treating physician.

Stable, therapeutic doses of anticoagulants are permitted. However, subjects on warfarin should have PT/INR/PTT monitored according to [Table 3](#) and as clinically indicated.

Subjects receiving recombinant erythropoietin or darbepoetin alfa for at least 4 weeks prior to starting IP treatment may continue their pretreatment doses throughout the study. However, as of April 2015, note that recombinant erythropoietin and darbepoetin alfa are not approved for the treatment of cancer chemotherapy associated anemia in Japan.

G-CSF may be used to mitigate the duration of neutropenia in the following situations:

- During Cycle 1: Grade 4 neutropenia lasting  $> 7$  days or associated with fever (such as after experiencing a DLT of neutropenia)
- After Cycle 1:  $\geq$  Grade 3 neutropenia

Note: G-CSF should not be administered concurrently (within 24 hours) with CC-122.

Flu vaccination is permitted.

Routine infectious disease prophylaxis is not recommended. However, antibiotic, antiviral, antipneumocystis, antifungal, or other prophylaxis may be implemented during the study at the discretion of the investigator.

Pneumocystis pneumonia (PCP) prophylaxis may be initiated with two consecutive confirmed CD4 measurements  $< 200 / \text{mm}^3$ .

Treatment with bisphosphonates (such as pamidronate, zolendronate), or other agents (such as denosumab) to prevent or delay progression of bone metastases are permitted. Maintenance of a stable dosing regimen throughout the study is recommended.

Subjects may receive physiologic replacement doses of glucocorticoids (up to the equivalent of 10 mg daily prednisone) as maintenance therapy for adrenal insufficiency.

Caution is recommended with the use of valproic acid due to the potential for drug interaction.

CC-122 absorbs ultraviolet (UV) light between the frequencies of 290 and 700 nm and has been shown to distribute to the skin and eyes in preclinical animal studies. As a precautionary measure, it is recommended that subjects avoid prolonged exposure to UV light, wear protective clothing and sunglasses, and use UV-blocking topical preparations while taking CC-122.

Subjects receiving CC-122 have developed venous thromboembolism/thromboembolism events reported as serious adverse events. Subjects and physicians are advised to be observant for the

signs and symptoms of thromboembolism. Subjects should be instructed to seek medical care if they develop symptoms, such as shortness of breath, chest pain, or arm or leg swelling. It is recommended that the investigator carefully assess an individual subject's underlying risk for thromboembolism and bleeding and consider prophylactic measures with anticoagulation or antiplatelet agents.

## **9.2. Prohibited Concomitant Medications and Procedures**

Other investigational therapies must not be used while the subject is on the study.

Anticancer therapy (chemotherapy, biologic or investigational therapy, and surgery) other than the study treatments must not be given to subjects during the study. If such treatment is required, the subject must be discontinued from the study.

However, focal palliative radiotherapy for treatment of cancer-related symptoms is allowed during study treatment at the discretion of the investigator.

## **9.3. Required Concomitant Medications and Procedures**

Every effort should be made to ensure that subjects are adequately hydrated prior to dosing.

Subjects who develop asymptomatic rises in TSH  $\geq 10$  mIU/L or symptomatic rises  $> 5$  mIU/L should receive supplementation with thyroxine according to local standard practice.

## 10. STATISTICAL ANALYSES

### 10.1. Overview

The primary objectives of the study are to determine the safety and tolerability of CC-122, to define the MTD and/or RP2D, and to determine the plasma PK of CC-122 when administered orally to adult Japanese subjects with advanced solid tumors or NHL. The secondary objective of the study is to make a preliminary assessment of the antitumor activity of CC-122. The exploratory objectives of the study include evaluating the plasma PK of CC-122 formulated capsules and compare results to the plasma PK of CC-122 AIC, assessing the tolerability of CC-122 formulated capsules, [REDACTED]

In the following, statistical analyses will be performed by dose level, visit cycle and tumor type as needed or applicable.

### 10.2. Study Population Definitions

The study population definitions are as follows:

- Enrolled Population – includes all subjects enrolled, such as all subjects who are assigned an enrollment number.
- Treated Population – all enrolled subjects who take at least one dose of CC-122.
- Efficacy Population – all subjects who complete at least one cycle of their assigned treatment regimen, and have a baseline and at least one post-baseline efficacy assessment.

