#### **3.2. Secondary Endpoint(s)**

The secondary endpoint of this study is:

- Antitumor efficacy, determined by response rates in each tumor type using appropriate tumor response criteria, and duration of response

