#### **4.1.1. Evaluation of Dose-limiting Toxicities**

Cohorts of at least 3 subjects (to 6 subjects) will be enrolled at each dose level.

After the first dose is administered to the last subject in any cohort, subjects are observed for at least 28 days (Cycle 1) during the DLT evaluation period before the next higher, protocol-specified dose level cohort can begin.

A standard escalation schedule will be initiated in order to establish the MTD or RP2D by assessing the occurrence of DLTs. Smaller increments and additional subjects within a dose cohort may also be evaluated as necessary to determine the MTD and RP2D more precisely.

A dose level will be considered tolerable if 0 of 3 treated subjects experiences a DLT during the DLT evaluation period for each respective group. If 1 of 3 subjects experiences a DLT, 3 additional subjects will be enrolled and treated at that dose level.

A dose will be considered an NTD when two or more out of six evaluable subjects in a cohort experience DLTs during the DLT evaluation period.

The MTD is defined as the last dose level below the NTD with zero or one out of six evaluable subjects experiencing DLTs during the DLT evaluation period. At least 6 subjects will be enrolled at the MTD/RP2D.

The decision to either evaluate a higher dose level or declare the MTD or RP2D will be determined by the Safety Review Committee (SRC), which includes the principal investigator and Celgene's medical monitor (see Section 8.2.1), each time all clinical and laboratory safety data for a given cohort are available for review.

The SRC may decide to identify an RP2D based on safety, PK, and preliminary efficacy information, which will not exceed the MTD from global CC-122 trials in various indications.

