**Table 6: Tumor Assessments**

Visit	Assessments
Screening	
Tumor assessments via imaging studies, including computed tomography (CT) and/or magnetic resonance imaging (MRI), of the chest and abdomen and pelvis (including other sites, as appropriate) [or fludeoxyglucose positron emission tomography (FDG-PET) as necessary] will be performed.
 
A brain scan (CT or MRI) will be performed for subjects with known brain lesions.
 
Bone marrow aspirate and biopsy (with cytogenetic analysis, as appropriate depending on cancer type) should be performed for subjects with known or suspected bone marrow involvement.
 
Note: Efficacy assessments (scans, aspirates, and biopsies) obtained within 8 weeks of the first dose of IP and prior to obtaining informed consent as part of standard of care assessments may be used, assuming these assessments meet the protocol requirements.

Day 15 of Cycle 2, 4, 6 and every 3 cycles thereafter (Cycles 9, 12, 15, etc.)  Allowable window: ( $\pm$ 7 days)	
Tumor assessments via imaging studies, including CT and/or MRI, of the chest and abdomen and pelvis (including other sites, as appropriate) [or FDG-PET as necessary] will be performed.
 
A brain scan (CT or MRI) will be performed for subjects with known brain lesions.
 
Bone marrow aspirate and biopsy (with cytogenetic analysis, as appropriate depending on cancer type) should be performed for subjects with known or suspected bone marrow involvement.

End of treatment (may be omitted if performed within the previous 28 days)	
Tumor assessments via imaging studies, including CT and/or MRI, of the chest and abdomen and pelvis (including other sites, as appropriate) [or FDG-PET as necessary] will be performed.
 
A brain scan (CT or MRI) will be performed for subjects with known brain lesions.
 
Bone marrow aspirate and biopsy (with cytogenetic analysis, as appropriate depending on cancer type) should be performed for subjects with known or suspected bone marrow involvement.

After screening, tumor assessments thereafter should be performed using the same CT/MRI scanning modalities used at screening, as permissible.

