### 8.2.7. Criteria for Dose Escalation in the Next Cohort of Subjects

Cohorts will consist of at least 3 or at least 6 evaluable subjects. The decision criteria for dose escalation in any cohort are:

- If no DLT is observed in at least 3 evaluable subjects during the first cycle, the dose will be considered a well-tolerated dose and dose escalation will continue to the next dose level.
- If any DLT is observed in 2 or more of 6 evaluable subjects in the cohort, this dose is considered a non-tolerated dose and dose escalation will discontinue.

- If any DLT is observed in one evaluable subject during the DLT evaluation period, additional subjects will be enrolled to expand the cohort to up to at least 6 evaluable subjects.

The number of cohorts depends on the incidence of DLTs. A subject may experience more than one DLT. Dose-escalation decisions are based on the number of subjects experiencing DLTs.

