### **8.2.9. Permitted Dosing Adjustments**

No dose reduction is allowed during the DLT evaluation period, except for subjects who experience DLTs. Subjects who experience DLTs during the DLT evaluation period will be allowed to resume CC-122 at a reduced dose once their toxicity recovers to Grade 1 or baseline, provided recovery occurs within 28 days of interrupting dosing. Dose reductions for non-dose-limiting toxicities are allowed after the DLT evaluation period after consultation with the sponsor.

Those continuing to take CC-122 beyond Cycle 1 may, following approval by the SRC, have their dose level increased, provided that the alternative dose level has been shown to be well-tolerated in at least one cohort of other subjects in this study. In these instances, additional PK evaluations at the higher dose level will be collected.

If a dose reduction is indicated, the next lower dose level will be selected. Two dose reductions are allowed, with the exception of the starting dose for which only one dose reduction is allowed. If any subject continues to experience unacceptable toxicity after 2 dose reductions, CC-122 will be discontinued permanently.

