#### **8.2.9.1. Criteria for Dose Reduction**

Dose reductions are not allowed during the DLT evaluation period, except for subjects who experience DLTs. Subjects who experience toxicities during the DLT evaluation period that do not meet the protocol specified definition for DLTs (Section 8.2.6) may either continue at their assigned dose or withdraw from the study at the discretion of the investigator and/or the subject. If a subject withdraws for any reason other than DLTs prior to the completion of the DLT evaluation period, that subject will be considered non-evaluable and will be replaced.

Once the dosage has been reduced for toxicity for a subject, future escalation will not be permitted.

Any of the AEs listed in [Table 10](#) after the DLT evaluation period will require a dose interruption and/or reduction.

Dose reductions may be considered for AEs occurring after the DLT evaluation period that do not meet the criteria listed in [Table 10](#) after discussion between the investigator and the sponsor.

Guidance for dose reduction is as follows:

- Subjects requiring dose reductions for toxicities occurring on or BEFORE Cycle 1 Day 28 (such as subjects who have experienced DLTs and recovered) should be reduced to the next lowest dose level that has been shown to be tolerated by at least 3/3 or 5/6 subjects.
- Subjects requiring dose reduction for toxicities occurring AFTER Cycle 1 Day 28 may be reduced to the next lowest dose level that has been shown to be tolerated by at least 3/3 or 5/6 subjects.

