## **10.6. Efficacy Analysis**

The efficacy population will be used for efficacy analysis. The efficacy variables of primary interest are tumor response. Tumor response (Appendix A, Section 19.1) will be based on investigator assessment using the Response Evaluation Criteria In Solid Tumors (RECIST) version 1.1 for solid tumors, and the International Workshop Group (IWG) Revised Criteria for Lymphoma. Subjects will be evaluated for tumor response on Day 15 of Cycle 2, 4, 6, and every 3 cycles thereafter. A descriptive analysis of evidence of antitumor activity will be provided based on clinical, laboratory and radiographic assessments performed by the investigator, which includes assessments of target lesions, non-target lesions, new lesions and overall response. Both confirmed and unconfirmed responses by RECIST version 1.1 will be assessed.

The efficacy variable of focus will be best overall response. Duration of response will also be assessed. The data analyses of other preliminary efficacy variables will be detailed in the Statistical analysis plan (SAP).

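### Response is analysed only in subjects who finish Cycle 1 and have a post-baseline assessment, so treated early failures leave the denominator and the reported rate will generally be too high

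*Combined protocol and SAP*

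**What the plan says.** The secondary endpoint in Section 3.2 is "Antitumor efficacy, determined by response rates in each tumor type using appropriate tumor response criteria, and duration of response".

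Section 10.2 defines three sets: Enrolled, Treated (at least one dose) and Efficacy. The Efficacy Population consists of subjects "who complete at least one cycle of their assigned treatment regimen, and have a baseline and at least one post-baseline efficacy assessment". Section 10.6 then states: "The efficacy population will be used for efficacy analysis". Its focus is best overall response. Only the other preliminary efficacy variables are deferred to the SAP, so the response set is fixed here. The Treated Population is used for baseline characteristics (Section 10.4), and the safety analyses apply the same one-dose rule (Section 10.7).

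Four further provisions decide who is affected:

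- **Timing of assessment.** The first scheduled post-baseline tumor assessment is Cycle 2 Day 15, with a window of 7 days either side (Table 6). None is scheduled in Cycle 1. Table 6 also has an end-of-treatment assessment: "End of treatment (may be omitted if performed within the previous 28 days").
- **Replacement.** A subject who withdraws during the DLT period for a reason other than a DLT falls under Section 8.2.9.1: "that subject will be considered non-evaluable and will be replaced".
- **DLT subjects.** A subject with a DLT is evaluable for DLT (Section 8.2.4) and is not replaced on that account. One DLT leads to expansion under Section 8.2.7: "additional subjects will be enrolled to expand the cohort to up to at least 6 evaluable subjects". After recovery such a subject "will be allowed to resume CC-122 at a reduced dose" (Section 8.2.9).
- **Use of the result.** Section 4.1.1 says: "The SRC may decide to identify an RP2D based on safety, PK, and preliminary efficacy information".

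**The concern.** Membership of the Efficacy Population depends on what happens after the first dose. The treated subjects it removes are those who stop in Cycle 1 because of death, a DLT, progression or withdrawal, and those who leave later with no post-baseline assessment. Most of them can be expected to be non-responders. Removing them shrinks the denominator and leaves the numerator alone.

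The two conditions act separately. A subject who progresses in Cycle 1 and has an end-of-treatment scan does have a post-baseline assessment, but still fails the one-cycle condition. A documented treatment failure is then left out. By contrast, a subject who completes Cycle 1 and has an end-of-treatment assessment is retained.

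Replacement makes the effect harder to see, because it refills the Efficacy Population while the replaced subject disappears from the rate.

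What is at stake is the accuracy of the secondary endpoint, and of any efficacy information the SRC weighs when it identifies the RP2D.

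**Working it through.** **The plan's own figure.** The only number to reproduce is the planned size. The minimum cohort sizes are 3 for each of Cohorts 1 to 3 (Section 4.1.1) and 6 for Cohort 4 (Section 4.1): 3 + 3 + 3 + 6 = 15, which matches the stated approximate 15. Section 10.3 says the size has no statistical basis. No response rate, exit rate or precision target is given, so all responder and exit counts below are assumptions.

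**Formula.** Let n be the number treated, x the responders, and k the treated non-responders outside the Efficacy Population. The reported rate is x/(n − k) and the all-treated rate is x/n. Their ratio is n/(n − k), which exceeds 1 whenever k > 0 and x > 0. If x = 0, both rates are 0%.

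**Case A: exits are replaced.** Assume an Efficacy Population of 15, 4 responders, and k replaced Cycle 1 exits, so n = 15 + k. The reported rate is always 4/15 = 26.7%.

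| k | All-treated rate | Reported minus all-treated (points) |
|---|---|---|
| 0 | 4/15 = 26.7% | 0 |
| 1 | 4/16 = 25.0% | 1.7 |
| 2 | 4/17 = 23.5% | 3.1 |
| 3 | 4/18 = 22.2% | 4.4 |
| 4 | 4/19 = 21.1% | 5.6 |
| 5 | 4/20 = 20.0% | 6.7 |

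**Case B: exits are not replaced.** Assume 15 treated in all.

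| x | All-treated rate | Reported, k = 1 | k = 2 | k = 3 | k = 4 |
|---|---|---|---|---|---|
| 3 | 3/15 = 20.0% | 3/14 = 21.4% | 3/13 = 23.1% | 3/12 = 25.0% | 3/11 = 27.3% |
| 5 | 5/15 = 33.3% | 5/14 = 35.7% | 5/13 = 38.5% | 5/12 = 41.7% | 5/11 = 45.5% |

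The rise is 1.4 to 7.3 points with 3 responders and 2.4 to 12.1 points with 5.

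**Case C: one cohort of 6.** Suppose the cohort was expanded after one DLT and the DLT subject left in Cycle 1. With 1 responder the rates are 1/5 = 20.0% reported and 1/6 = 16.7% all-treated. With 3 responders they are 3/5 = 60.0% and 3/6 = 50.0%. Small denominators matter because the endpoint is reported by tumor type, and Section 10.1 allows analysis by dose level.

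**Case D: the opposite direction.** The plan does not say whether a DLT subject who resumes at a reduced dose has completed a cycle of the assigned regimen. If such a subject is excluded and is one of 4 responders among 16 treated, the reported rate is 3/15 = 20.0% against 4/16 = 25.0% all-treated. This is why the bias is generally, and not always, upward.

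**Scale against sampling error.** The exact (Clopper-Pearson) 95% interval is 7.8% to 55.1% for 4/15, a width of 47.3 points, and 5.7% to 43.7% for 4/20.

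**The case against.** The strongest opposing case is about consequence.

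- **Size.** Response is a preliminary, descriptive secondary endpoint with no hypothesis test, and its sampling error is much larger than the bias. This stands. It limits the weight of the point but does not justify keeping the rule, since interval width does not cancel an avoidable shift in the estimate.
- **The RP2D link.** Section 8.2.1 has the SRC review safety and available PK at the end of the DLT period, usually before the latest cohort's first scheduled scan. Nothing says the SRC would use the Section 10.6 rate and not individual data, in which early exits are visible. This stands in part: Section 4.1.1 permits the use of preliminary efficacy, but an effect on the RP2D is only a possibility.
- **Assumed magnitudes.** The size depends on the scenario. Case A assumes every exit is replaced, which does not fit DLT exits; Case C covers those. Five exits has no basis in the documents, and 4/15 pools tumor types although the endpoint is by tumor type. The justification for Amendment 03 reports safety confirmed at the first three dose levels and some subjects on study for up to 12 cycles, so exits may be few. All of this stands: the figures are illustrations. The direction when non-responders are excluded does not depend on the scenario.
- **Disclosure.** Section 10.5 tabulates population allocation and reasons for discontinuation, so a reader could largely rebuild the wider denominator. True, but the published rate would still omit these subjects.
- **A prespecified choice.** An evaluable set is openly defined and contradicts nothing in the plan. That is fair, but stating a selective rule in advance does not make it unbiased.
- **Unseen text.** No separate SAP text is included, and the response criteria are incorporated only by citation. This is a modest limit, because Section 10.6 defers only other efficacy variables.

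**Conclusion.** The concern holds. By a stated rule, the only set used for response drops treated subjects who stop in Cycle 1 or have no post-baseline assessment, and nothing in the documents counts them as non-responders. If one or more such non-responders exist and at least one subject responds, the reported rate is too high by the factor n/(n − k). In the assumed examples this is 1.7 to 6.7 points for 1 to 5 replaced exits, up to 12.1 points for 4 unreplaced exits with 5 responders, and 10 points for one exclusion from a cohort of 6 with 3 responders. There is no effect without exits or without responders, and it can reverse if an excluded subject responded. The correction is worth making to a reported secondary result. It does not bear on the primary safety, MTD or PK objectives.

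**What to change.** In Sections 10.2 and 10.6, make the Treated Population the main set for best overall response and response rate, counting any treated subject with no post-baseline assessment as a non-responder. Keep the present Efficacy Population as a supportive analysis. For that supportive set, state whether a subject whose dose was interrupted or reduced in Cycle 1 counts as having completed a cycle of the assigned regimen.

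The cost is wording in two sections and one extra table. The Treated Population is already defined and no new data are needed. The headline response rate may come out lower.
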